6.2 Sample Size and Power

Sample Size and Power: This is a longitudinal study of the effects of ivacaftor treatment on outcomes before and after 12-week treatment. The sample size of 16 subjects to complete the study has been determined as adequate to have the power to test the primary outcomes of decrease in SEE percent predicted value (7% change), an increase in BMI Z score of 0.3, and secondary outcomes of measures of gut health and function; an increase in plasma total fatty acids from 8.5 to 10.5 mmol/L, an increase in fecal elastase of 120 ug/g stool, and a decrease in fecal calprotectin (-30 ug/g stool change). Using STATA, power calculations were generated, with α =0.05, for paired data (n=16) within the same sample (before and after 12 weeks of treatment) using the changes described above for the primary outcomes and secondary outcomes.

Primary outcomes: A sample size of 16 subjects results in 86% power to see a decrease of 7% in **SEE** (i.e. from 115 to 108) with a standard deviation of the change of 9%, using a paired t-test two-sided significance level. We demonstrated a change of similar magnitude in REE in 24 subjects with CF gating mutation after 3-mo treatment with ivacaftor^{7,9}. For growth status, 16 subjects will provide 85% power to detect an increase in **BMI Z score** of 0.3 with a standard deviation of 0.4. In the KIWI study of 2 to 5 year old children with CFTR gating mutation treated with ivacaftor for 24 weeks, a BMIZ score increase of 0.4±0.4 was demonstrated⁶. We showed a BMI Z score increase over 12 weeks of 0.3±0.4 in our recent study of 18 children (5 to 19 years) with 12-week ivacaftor treatment⁷.

Secondary outcomes: A sample of 16 subjects will provide 80% power to detect an increase in total plasma fatty acids from 8.5 to 10.5 mmol/L with a standard deviation of 2.8%, will provide 88% power to detect an increase in fecal elastase of 120 ug/g stool with a standard deviation of 150 ug/g stool, and will provide 85% power to detect a decrease in fecal calprotectin of 30 ug/g stool with a standard deviation of the change of 40 ug/g stool. We previously demonstrated a 3-month increase in plasma total fatty acids of this magnitude in subjects with CF receiving a fat-based nutritional supplement¹⁹. Davies et al⁶ demonstrated a change of 100 ug/g stool in fecal elastase with 24-week ivacaftor treatment in for 2 to 5 year old children with CFTR gating mutations in the KIWI study, and an even greater increase of 164 ug/g stool fecal elastase was shown in 1 to 2 year old children participating in the ARRIVAL study¹⁶. We have previously demonstrated a 3-month decrease of 30 ug/g stool in fecal calprotectin with ivacaftor treatment in 5 to 61 year old people with CFTR gating mutations⁷. The standard deviations of 9% for SEE, 40 ug/g stool for fecal calprotectin, 150 ug/g stool for fecal elastase and 0.4 for BMI Z score are reasonable estimates of the variability expected in changes for these variables from our experience with 3-12 month changes in these measures in previous longitudinal clinical trials we have conducted for changes in children and adults with CF^{7,18,19,37,38}. In addition, our recent experience with SEE measures in 1 year old healthy children showed a standard deviation of 8% in SEE percent predicted values³⁹ (personal communication).

We plan for up to 12% attrition over the 12 weeks. By enrolling 18 subjects we can account for attrition and also allow for the possibility of greater variability in the SEE, BMI Z scores and gut health and function measures.

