Objectives: The primary aims of the study are to evaluate the impact of 12 weeks of ivacaftor treatment in 6 month to 2 year old subjects with CF and gating mutations growth status and gut health and function in n=18 children with protocol evaluations at baseline (pre-treatment) and 6 and 12 weeks after clinically prescribed ivacaftor treatment has begun. Other outcomes of significant clinical interest in young patients with CF will be explored. All subjects will be evaluated at The Children's Hospital of Philadelphia, and will be recruited both regionally and nationally to ensure timely enrollment.

Study Design: Observational prospective study with evaluations before and after 12 weeks of ivacaftor treatment. An interim assessment at 6 weeks will also be included.

Setting/Participants: Eighteen subjects ages 6 months to 2 years of age cystic fibrosis and CFTR gating mutations who are in a general state of good health from cystic fibrosis centers in US and Canada.

Study Interventions and Measures: Subjects will be evaluated before and after ivacaftor treatment for sleeping energy expenditure, BMI Z score, gut health and function as indicated by plasma fatty acids, fecal elastase and fecal calprotectin. Dietary intake, growth status and velocity, and serum fat soluble vitamins, bile acids and calprotectin will also be assessed.

PROTOCOL SYNOPSIS

Study Title	Nutritional Impact of Ivacaftor Treatment in 6 month to 2 Year Old Children with CF Gating Mutations
Funder	Vertex Pharmaceutical and CHOP Center for Human Phenomic Science and Nutrition Center

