2.1 Primary Aims

H1: Ivacaftor treatment will result in a significant reduction in SEE as percent predicted over 12 weeks compared to baseline, thereby increasing the energy available for weight gain and physical activity.

H2: Ivacaftor treatment will result in significantly increased BMI Z score over 12 weeks compared to baseline.

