2.2 Secondary Aims

H3: Ivacaftor treatment will result in significantly improved gut health and function resulting in better dietary fat absorption as indicated by increased total plasma fatty acids and fecal elastase and decreased fecal calprotectin over 12 weeks compared to baseline.To determine if treatment with Ivacaftor results in increased dietary fat absorption using three methods:

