3.2.2 Total Number of Study Sites/Total Number of Subjects Projected

The study will be conducted at one investigative site in the United States.

Recruitment will stop when 18 subjects are enrolled. It is expected that 18 subjects will be enrolled to produce 16 evaluable subjects.

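### Two primary hypotheses are each tested two-sided at 0.05 with no success rule and no multiplicity control; if either alone counts as success, the familywise two-sided error is about 8% to 9.75%.

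*Combined protocol and SAP*

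**What the plan says.** Section 2.1 sets out two primary hypotheses, each worded in terms of statistical significance. H1 is a reduction in SEE percent predicted. The other reads "H2: Ivacaftor treatment will result in significantly increased BMI Z score over 12 weeks compared to baseline". Section 2.2 adds one secondary hypothesis, H3, read from three markers: "increased total plasma fatty acids and fecal elastase and decreased fecal calprotectin".

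Section 6.2 gives one alpha, "with α =0.05, for paired data (n=16", and applies it to each outcome in turn. For SEE it names the test and its sidedness: "using a paired t-test two-sided significance level". The printed powers are 86% for SEE and 85% for BMI Z.

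Section 6.1.1 analyses each outcome with its own paired t-test (or Wilcoxon signed-rank test), followed by mixed models over the three visits. It states no significance level, no testing order, no adjustment, and no rule on whether one or both primary outcomes must succeed.

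The Objectives paragraph of the Abstract describes the primary aims differently, as the effect on "growth status and gut health and function in n=18 children". That includes gut health and leaves out SEE, whereas sections 2.1 and 2.2 make SEE primary and gut health secondary.

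**The concern.** With two primary hypotheses, the reader needs to know what counts as a positive study. The plan is silent, so three readings are open after the data are seen: either outcome suffices, both are required, or each is a separate question with its own 5% error. They carry different error rates and different power. If either outcome suffices, two tests at 0.05 give a familywise error well above 5%. If both are required, the error is controlled, but the chance of success is far below the powers printed for the individual outcomes.

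The study is single-arm with 16 evaluable children, so no control group is available to temper a chance finding. The Abstract's different list of primary aims makes it less clear which results could later be called primary.

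**Working it through.** **Inputs.** From section 6.2: two-sided paired t-test, alpha 0.05, n=16 completers; SEE change 7 with SD of change 9; BMI Z change 0.3 with SD 0.4. Section 3.2.2 is consistent with this n: "It is expected that 18 subjects will be enrolled to produce 16 evaluable subjects". So is the allowance for up to 12% attrition: 18 × 0.88 = 15.84, or about 16. The documents give no correlation between the two changes. I assume 0 to 0.8 in the direction of benefit, since section 1.1 expects growth to improve as SEE falls.

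**1. The printed powers.** The noncentrality is (change/SD) × √16.
- SEE: (7/9) × 4 = 3.111. BMI Z: (0.3/0.4) × 4 = 3.000.
- Normal approximation, Φ(noncentrality − 1.960): SEE Φ(1.151) = 87.5%; BMI Z Φ(1.040) = 85.1%. These lie within 2 points of the printed 86% and 85%.
- Paired t-test at n=16 (15 degrees of freedom, critical value 2.131, noncentral t): SEE 82.8%, BMI Z 80.1%.
- Paired t-test at n=18: 87.5% and 85.0%.

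The printed values therefore fit a normal approximation at n=16, or a t-test at n=18. The named t-test at n=16 delivers about 3 and 5 points less.

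**2. Familywise error if either outcome suffices, both nulls true.**
- Independent changes: 1 − 0.95² = 9.75%.
- Correlated changes (simulated paired t-tests, n=16): about 9.2% at 0.5 and about 8% at 0.8.
- False claims of improvement only: 1 − 0.975² = 4.9% if independent; about 4.6% at 0.5 and 4.0% at 0.8.
- Holm (smaller p-value against 0.025, then the other against 0.05) holds the two-sided rate at or below 5%: about 4.9% if independent and 4.1% at 0.8.

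**3. Power under Holm, paired t-test, n=16.** At alpha 0.025, power is 72.75% (SEE) and 69.29% (BMI Z). With independent changes, an outcome's Holm power is P(p<0.025) + P(0.025≤p<0.05) × P(other p<0.025).
- Both effects real, SEE: 0.7275 + (0.8282 − 0.7275) × 0.6929 = 79.7%.
- Both effects real, BMI Z: 0.6929 + (0.8006 − 0.6929) × 0.7275 = 77.1%.
- Only SEE real: 0.7275 + 0.1007 × 0.025 = 73.0%.
- Only BMI Z real: 0.6929 + 0.1077 × 0.025 = 69.6%.

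| Scenario | SEE | BMI Z | Loss (points) |
|---|---|---|---|
| Unadjusted | 82.8% | 80.1% | – |
| Holm, both real, independent | 79.7% | 77.1% | about 3 |
| Holm, both real, correlation 0.5 | about 78.5% | about 76% | about 4 |
| Holm, both real, correlation 0.8 | about 77% | about 75% | about 5 to 6 |
| Holm, only that effect real | 73.0% | 69.6% | about 10 |

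**4. If both outcomes are required.** No adjustment is needed. Joint power with independent changes is 0.828 × 0.801 = 66%; by simulation it is about 70% at correlation 0.5 and 74% at 0.8.

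**The case against.** Four objections deserve an answer.

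*The plan never promises a familywise 5%.* This is correct. Alpha appears only in the power section, and the goal in section 6.1.1 can be read as improvement in both outcomes. A reader might infer that either outcome alone would be reported as a positive primary result, but the documents do not say so. What stands is the missing rule, and the error rates above are conditional on it.

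*H1 and H2 are directional.* Also correct. A reader might infer that the chance of falsely claiming a benefit is nearly 10%. It is not: with two-sided tests, false claims of improvement on at least one outcome occur in about 4.9% of trials or fewer. The figure near 10% counts false significance in either direction, which is the usual convention for the two-sided tests the plan names.

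*Correction costs power in a small study.* It does. A reader might infer that Holm costs only about 3 points. That holds only if both planned effects are real and the changes are independent. Against the printed 86% and 85%, the best-case Holm powers are about 6 and 8 points lower, but roughly half or more of that gap comes from the power method and not from multiplicity.

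*H3 also rests on three tests without a combining rule.* True, but these are secondary outcomes in an 18-child observational study. Nothing in the documents makes formal adjustment there a requirement; reporting each outcome separately is enough.

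**Conclusion.** The concern holds in a limited form. Two primary hypotheses are each tested two-sided at 0.05, with neither a success rule nor multiplicity control. If either alone counts as success, the familywise two-sided error is 9.75% with independent changes and about 8% at correlation 0.8, assuming both nulls are true. Holm removes the excess at a price that depends on which effects are real and how the changes correlate. If both outcomes must succeed, there is no error inflation, but the study has about 66% power for that result (independent changes, planned effects and SDs), which the plan does not disclose. Separately, the printed powers of 86% and 85% overstate the named test at n=16.

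**What to change.** 1. In section 6.1.1, state whether one or both primary outcomes must succeed. If either suffices, prespecify Holm for H1 and H2. If both are required, say so, use no adjustment, and state the joint power of about 66% with its independence assumption.
2. In section 6.2, replace the printed primary powers with those for the paired t-test at n=16 (82.8% and 80.1%). If Holm is adopted, add the Holm range from the table with its conditions.
3. Align the Abstract's primary aims with section 2.1.
4. Report the three H3 outcomes separately, not as one gut-health verdict; adjusting them is optional.

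The cost is wording and restated power, with no extra patients. Under Holm, the real price is a loss of about 3 to 10 points of power per primary outcome, largest when only one outcome responds.

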6.1.1 Analysis of Primary & Secondary Aims

Data Analysis: Analysis will begin with descriptive analyses of the study sample using means, standard deviations, medians, and ranges for continuous variables, and frequency distributions for categorical variables. Descriptive statistics and exploratory graphing such as frequencies, means, standard deviations, box plots, and scatter plots will be used to assess the normality of the data in terms of the presence of skew and/or outliers. Primary Aims: The goals of the primary aims of this study are to determine whether ivacaftor treatment improves SEE and BMI Z score. Secondary Aims: The goal of the secondary aim is to determine whether ivacaftor improves gut health and function as measured by total plasma fatty acids, fecal elastase and fecal calprotectin (ug/g stool). Analysis of efficacy for the primary and secondary outcomes will be based on change from baseline (before treatment) in SEE% predicted (Schofield), BMI Z scores, total plasma fatty acids, fecal elastase continuous

outcomes will initially be compared using paired-t-tests if continuous variables are normally distributed and nonparametric tests (Wilcoxon sign rank) if they are not. Subsequently, mixed effects longitudinal models will be performed to assess change over all three time points (baseline, 6 and 12 weeks), adjusting for potential covariates such as age, sex, and adherence to treatment. Chi-squared tests will be used for comparison of categorical variables before and after ivacaftor treatment. Using similar methods, exploratory analyses will examine improvement in dietary intake of calories and fat, in growth status (weight, length, and head circumference Z scores) and growth velocity (both absolute and Z scores), serum fat soluble vitamins, bile acids, and calprotectin.

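### The powers in section 6.2 are 3 to 5 points higher than the named two-sided paired t-test gives at n=16, and the fatty-acid SD is printed as a percentage

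*Combined protocol and SAP*

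**What the plan says.** Section 6.2 (Sample Size and Power) sets alpha at 0.05 with paired data on 16 children, and gives five powers:

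- **SEE % predicted (primary):** "A sample size of 16 subjects results in 86% power to see a decrease of 7"%, SD of the change 9%, "using a paired t-test two-sided significance level".
- **BMI Z (primary):** "16 subjects will provide 85% power to detect an increase in" BMI Z of 0.3, SD 0.4.
- **Total plasma fatty acids (secondary):** "A sample of 16 subjects will provide 80% power to detect an increase in total plasma fatty acids from 8.5 to 10.5 mmol/L". The SD for this outcome is printed as 2.8 followed by a percent sign.
- **Fecal elastase (secondary):** "will provide 88% power to detect an increase in fecal elastase of 120 ug/g stool with a standard deviation of 150 ug/g stool".
- **Fecal calprotectin (secondary):** "will provide 85% power to detect a decrease in fecal calprotectin of 30 ug/g stool", SD of the change 40 ug/g.

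Section 6.2 later describes the SDs for SEE, BMI Z, elastase and calprotectin as variability of changes, based on the investigators' earlier studies. The fatty-acid SD is not in that sentence.

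The planned analysis in section 6.1.1 agrees with the named test: "outcomes will initially be compared using paired-t-tests if continuous variables are normally distributed", with the Wilcoxon signed-rank test otherwise.

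Section 3.2.2 expects 18 enrolled to yield 16 evaluable. Section 6.2 allows for attrition of up to 12% and says that enrolling 18 also leaves room for greater variability in the outcomes.

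**The concern.** With 16 pairs the t-test has only 15 degrees of freedom, so treating the SD as known overstates power noticeably. The printed powers look like the result of such a shortcut, or of a calculation at 18 children, although the text says t-test and 16.

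These figures are the stated justification for the sample size. If they are too high, a reader sees a five-point reserve above 80% for BMI Z (a primary outcome) and calprotectin that the design does not have. The fatty-acid power cannot be checked at all as printed, because a percentage is not a usable SD for an outcome in mmol/L.

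**Working it through.** **Inputs (section 6.2).** n = 16, two-sided alpha = 0.05. Effect / SD of change: SEE 7/9 = 0.778; BMI Z 0.3/0.4 = 0.75; elastase 120/150 = 0.80; calprotectin 30/40 = 0.75. For fatty acids the effect is 10.5 − 8.5 = 2.0 mmol/L. Reading the SD as an SD of change of 2.8 mmol/L (an assumption) gives 2.0/2.8 = 0.714.

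**Route that comes close to the printed figures.** Normal approximation with known SD: power = Φ(d√n − 1.96). For BMI Z, Φ(0.75 × 4 − 1.96) = Φ(1.04) = 85.1%, against a printed 85%.

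**Named test.** Paired t-test: noncentral t with n − 1 degrees of freedom and noncentrality d√n. For BMI Z at n = 16: noncentrality 3.0, 15 degrees of freedom, critical value 2.131, power 80.1%.

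| Outcome | Stated | Paired t, n=16 | Gap (points) | Normal approx., n=16 | Paired t, n=17 | Paired t, n=18 |
|---|---|---|---|---|---|---|
| SEE | 86% | 82.8% | 3.2 | 87.5% | 85.3% | 87.5% |
| BMI Z | 85% | 80.1% | 4.9 | 85.1% | 82.7% | 85.0% |
| Elastase | 88% | 84.8% | 3.2 | 89.2% | 87.2% | 89.2% |
| Calprotectin | 85% | 80.1% | 4.9 | 85.1% | 82.7% | 85.0% |
| Fatty acids (SD of change 2.8 mmol/L assumed) | 80% | 76.1% | 3.9 | 81.5% | 79.0% | 81.5% |

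Under the t-test each stated power is first reached at 18 evaluable children, which is full enrolment with no attrition.

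**Could rounding of the printed SD explain it?** The SDs of change that give the stated power by t-test at n = 16 are 8.60 (SEE, printed 9), 0.374 (BMI Z, printed 0.4), 143 (elastase, printed 150) and 37.4 (calprotectin, printed 40). Rounding could explain the first two. With the effects as printed, it explains elastase only if the SD was rounded more coarsely than to the nearest 10 (an SD of 145 gives 87.1%), and calprotectin only if more coarsely than to the nearest 1 (39.5 gives 81.0%).

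**Fatty-acid SD.** If 2.8 mmol/L is instead a per-visit SD, the SD of change is 2.8√(2(1 − r)). For assumed correlations r of 0.3, 0.5 and 0.7 this is 3.31, 2.80 and 2.17 mmol/L, with power 61.7%, 76.1% and 93.1% at n = 16. Read literally, 2.8% of 8.5 to 10.5 mmol/L is about 0.24 to 0.29 mmol/L and power is essentially 100%, so the printed unit does not fit the printed 80%.

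**Allowance for greater variability.** 18 × 0.88 = 15.84, so about 16 remain at the attrition ceiling. The largest SD of change that keeps 80% power:

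| Outcome | Planned SD | 16 evaluable | 18 evaluable |
|---|---|---|---|
| SEE | 9 | 9.3 | 10.0 |
| BMI Z | 0.4 | 0.40 | 0.43 |
| Elastase (ug/g) | 150 | 160 | 171 |
| Calprotectin (ug/g) | 40 | 40 | 42.8 |

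**Supporting statements.** Section 6.2 calls the 7% SEE change comparable to an REE result in 24 subjects. The synopsis rationale and section 1.1 report a 5.5% fall in a study of 23; the documents do not show whether this is the same result. Section 6.2 also says a fatty-acid rise of the planned size (2.0 mmol/L) was seen before, while section 1.1 gives 8.5 to 10.2, a rise of 1.7. At n = 16 with the SDs above, 5.5/9 gives 62.8% power, and 1.7/2.8 gives 62.2% under the same fatty-acid assumption.

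**The case against.** The arithmetic is not in dispute; the objections concern certainty and weight.

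- **Rounding.** For the two primary outcomes, unrounded SDs could reproduce the stated powers. If effects as well as SDs were rounded, elastase at 123/147 gives 87.8% and calprotectin at 31/38.6 gives 85.1%. The documents cannot exclude this. It does not rescue the text: the planned changes are printed as exact targets, and figures that cannot be obtained from the printed inputs and named test still need correcting or explaining. It does mean the sponsor should be free to supply the true inputs instead.
- **No decision changes.** This is right for the sample size. All four outcomes with a usable SD stay at or above 80%.
- **80% is not a stated target, and attrition may be below 12%.** Both are fair. With 17 or 18 children there is some room, so the enrolment sentence is too broad at the ceiling rather than false.
- **The comparisons with earlier results are loosely worded, and the cited sources are not available here.** This also stands. They are a request for clarification and carry no weight in the power finding.
- **The recomputed powers hold only for the t-test branch.** True. Section 6.1.1 switches to Wilcoxon if data are not normal and then fits mixed models, so restated figures should be labelled as paired t-test powers.

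**Conclusion.** The concern holds. For the named test at n = 16, the printed powers are overstated by 3.2 points (SEE), 4.9 (BMI Z), 3.2 (elastase) and 4.9 (calprotectin). This rests only on the printed effects and on SDs that section 6.2 itself identifies as SDs of change. The fatty-acid overstatement of 3.9 points depends on the assumed reading of the SD and cannot be confirmed until its unit and meaning are given.

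The documents do not show which calculation was run. The sample size does not need to change. BMI Z and calprotectin sit at 80% with no margin at 16 evaluable, and one further loss takes each to 77.1% at n = 15. This should be fixed because the figures are the plan's stated justification and anyone can check them.

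**What to change.** In section 6.2:

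1. Either print the unrounded inputs, or declare the normal approximation, if that is how the figures were obtained; or restate the paired t-test powers at n = 16 as 83% (SEE), 80% (BMI Z), 85% (elastase) and 80% (calprotectin). State 76% for fatty acids only if the SD is confirmed as a 2.8 mmol/L SD of change; otherwise recompute.
2. Correct the unit of the fatty-acid SD, say whether it is an SD of change, and give its source.
3. Reconcile the 7% change and 24 subjects with the 5.5% and 23 subjects in section 1.1 and the synopsis, and the 2.0 mmol/L rise with the 1.7 mmol/L in section 1.1. Sensitivity powers at the smaller effects are optional.
4. Qualify the enrolment sentence, for example: If attrition reaches 12%, about 16 children remain; at 80% power BMI Z and fecal calprotectin then have no allowance for greater variability, and SEE and fecal elastase keep a small one (SD of change up to about 9.3 and 160 ug/g). Add fatty acids once its SD is settled.

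The cost is wording in one section. No extra children are needed, and endpoints and analysis are unchanged. If the powers are restated, they become 3 to 5 points less favourable.

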	In our recent longitudinal observational study of 23 subjects (ages 5 to 61 years), we identified several mechanisms for weight gain with 3-month ivacaftor treatment including decreased resting energy expenditure (REE), gut inflammation and dietary fat malabsorption, resulting in a positive energy balance and weight gain. Weight gain in this study was 2.5 kg and was associated with a significant decrease in REE percent predicted of 5.5%, and in fecal calprotectin of 30 ug/g stool, a measure of gut inflammation ⁷⁻⁹ .
	Several outcomes related to improved energy balance are considered in this proposal. Building on our results in older

	subjects, we will once again focus on the importance of determining the effect of ivacaftor treatment on clinically important non- pulmonary outcomes. Our primary aim in this study of young 6 month to 2 year old children is to determine if 12-week ivacaftor treatment results in decreased sleeping energy expenditure (REE) and improved growth status by BMI Z score. Our secondary aim is to determine improvement in gut health and function associated with fat digestion, including increased total plasma fatty acids and fecal elastase, and decreased fecal calprotectin. Exploratory aims include investigating the impact of ivacaftor treatment on dietary intake, length, weight and head circumference status and growth velocity, and on serum fat soluble vitamins, bile acids and calprotectin.
Study Objective(s)	We propose a longitudinal study design to determine whether 12 weeks of treatment with ivacaftor results in improvement in sleeping energy expenditure (SEE), growth status as BMI Z score, and gut health and function in n=18 children ages 6 months to 2 years with at least one CFTR gating mutation. We anticipate that these changes will accompany meaningful improvements in dietary intake, growth status and growth velocity, and serum fat soluble vitamins, bile acids and serum calprotectin in these young children.
	PRIMARY AIMS
	H1: Ivacaftor treatment will result in a significant reduction in SEE as percent predicted over 12 weeks compared to baseline, thereby increasing the energy available for weight gain and physical activity.
	H2: Ivacaftor treatment will result in significantly increased BMI Z score over 12 weeks compared to baseline.
	SECONDARY AIMS

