Ivacaftor has shown similar benefit in younger children and has been approved for use in children 6 months and older.. Ivacaftor was found to be safe and effective in 33 children in the KIWI study completed 24 weeks of treatment in the KIWI study, with significant reductions in sweat chloride concentration, and an average increase in weight Z score of 0.2 ± 0.3 and BMI z score of 0.4 ± 0.4^6 . Some exocrine pancreatic function restoration was demonstrated in these young children, as Davies et al.⁶ noted an increase in fecal elastase concentrations in a small sample of children after 24 weeks ivacaftor treatment. Prior to treatment, 93% were PI with fecal elastase concentrations of <50 µg/g, and after treatment this increased 100 µg/g on average. Furthermore, in the KLIMB study, a long-term follow-up to the KIWI study, the increased fecal elastase concentrations were sustained with mean increase of 129 µg/g after 84 weeks of treatment¹⁴. These results suggest that exocrine pancreatic function early in life may be partially restored with ivacaftor^{6,15}.

In a recent open-label Phase 3 trial (the ARRIVAL study)^{16,17} in 18 children ages 1 to 2 years of age with CFTR gating mutations (G551D, G178R, S549N, S549R, G551S,

G1244E, S1251N, S1255P, G1439D, or R117H) who completed 24-weeks of treatment, ivacaftor was safe and effective in significantly reducing sweat chloride concentrations from 104.1 to 31.5 mmol/L, and improving (restoring) pancreatic function as indicated by increasing fecal elastase from 182 to 357 ug/g stool. Ivacaftor's impact on growth status or velocity for weight and BMI in these young children was not reported. Changes in energy expenditure with ivacaftor treatment in these young children has also not yet been explored. This current application will directly ddress gaps in knowledge related to the important non-pulmonary outcomes that are clinically very important in very young children.

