In our recent longitudinal observational study of 23 subjects (ages 5 to 61 years), we identified several mechanisms for weight gain with 3-month ivacaftor treatment including decreased resting energy expenditure (REE), gut inflammation and dietary fat malabsorption, resulting in a positive energy balance and weight gain. Weight gain in this study was 2.5 kg and was associated with a significant decrease in REE percent predicted of 5.5%, and in fecal calprotectin of 30 ug/g stool, a measure of gut inflammation⁷⁻⁹. For the 16 subjects with PI, dietary fat absorption as measured by coefficient of fat absorption (CFA) improved 3%^{7,8,18}. Dietary fat intake increased significantly in all subjects⁷, and energy intake increased, particularly in those from Italy⁸. In subjects <20 years of age, improved weight and BMI status was accompanied by beneficial effects on muscle mass, muscle function and QOL. Improvement in pancreatic function (fecal elastase) was seen in 5 of 7 subjects with PS. Whether a similar improvement in REE, growth status and gut health and function related to improved fat absorption in young children with CFTR gating mutations is not known.

Several outcomes related to improved energy balance are considered in this proposal. Building on our results in older subjects, we will once again focus on the importance of determining the effect of ivacaftor treatment on clinically important non-pulmonary outcomes. Our primary aim in this study of young 6 month to 2 year old children is to determine if 12-week ivacaftor treatment results in decreased sleeping energy expenditure (REE) and improved growth status by BMI Z score. Our secondary aim is to determine improvement in gut health and function associated with fat digestion, including increased total plasma fatty acids and fecal elastase, and decreased fecal calprotectin. Exploratory aims include investigating the impact of ivacaftor treatment on dietary intake, length, weight and head circumference status and growth velocity, and on serum fat soluble vitamins, bile acids and calprotectin.

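### All five powers in Section 6.2 exceed what the planned paired t-test gives at n=16 on the printed inputs, by 3.2 to 4.9 points (fatty acids if the SD is 2.8 mmol/L)

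*Combined protocol and SAP*

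**What the plan says.** **Power.** For the first primary outcome, Section 6.2 says "A sample size of 16 subjects results in 86% power to see a decrease of 7% in" SEE percent predicted (115 to 108), "with a standard deviation of the change of 9%, using a paired t-test two-sided significance level". At the same n of 16 and alpha of 0.05 for paired data, it also states:

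- BMI Z (the other primary outcome): +0.3, SD 0.4, 85%
- total plasma fatty acids: 8.5 to 10.5 mmol/L, SD printed as 2.8%, 80%
- fecal elastase: +120 ug/g, SD 150, 88%
- fecal calprotectin: -30 ug/g, SD 40, 85%

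**Analysis.** The synopsis and Section 6.1.1 compare baseline with 12 weeks by paired t-test for primary and secondary outcomes alike. A Wilcoxon signed-rank test is used if the data are not normal, and mixed models follow.

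**Sample.** Section 3.2.2: "It is expected that 18 subjects will be enrolled to produce 16 evaluable subjects". Section 6.2 allows for up to 12% attrition.

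**Source of the SEE effect.** Section 6.2: "We demonstrated a change of similar magnitude in REE in 24 subjects with CF gating mutation after 3-mo treatment with ivacaftor". No size is given there. The synopsis (Study Rationale) and Section 1.1 describe what may be the same work: "In our recent longitudinal observational study of 23 subjects (ages 5 to 61 years"), with weight gain "associated with a significant decrease in REE percent predicted of 5.5" percent. Of the new age group, Section 1.1 says: "Changes in energy expenditure with ivacaftor treatment in these young children has also not yet been explored".

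**Source of the fatty acid effect.** Section 6.2 says an increase of the planned size was seen in a supplement trial (reference 19). Section 1.1 reports that trial's change as 8.5 to 10.2 mmol/L.

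**The concern.** The stated powers should follow from the printed effect, SD, n and test. For SEE they do not: the paired t-test is named, and it gives a lower figure. A slip in one outcome could be rounding, but the same upward shift in all five suggests that another method or another n was used.

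SEE and BMI Z are the two primary outcomes. A reader facing a non-significant result will judge it by the stated power. For SEE, the chance of missing the planned effect is 17% rather than 14%; for BMI Z it is 20% rather than 15%.

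The second matter is the basis of the planned effects. Section 6.2 prints the size of the prior result for BMI Z, elastase and calprotectin. For SEE and fatty acids it only calls the prior change similar, and the figures elsewhere in the document are smaller than those planned.

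**Working it through.** **Inputs.** Effects, SDs, alpha 0.05 two-sided and n=16 are from Section 6.2; n=18 is the enrolment in Section 3.2.2. The fatty acid SD is taken as 2.8 mmol/L for the change, which is an assumption because the printed unit is a percentage.

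**Formulas.** λ = (effect / SD) × √n, with √16 = 4.

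- Paired t-test: power = P(|T| > 2.131), where T is noncentral t with 15 df and noncentrality λ.
- Normal approximation: power = Φ(λ − 1.960).

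**SEE, stated 86%.** λ = 7/9 × 4 = 3.111.

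- Paired t: 82.8% (82.9% in a simulation of 400,000 samples).
- Normal approximation: Φ(1.151) = 87.5%.
- Paired t at n=17: 85.3%; at n=18: 87.5%.

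So 86% is not obtained exactly by either method at n=16 with an SD of 9.0.

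**All five outcomes.**

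| Outcome | Effect / SD | λ at 16 | Stated | Paired t, n=16 | Gap (points) | Normal, n=16 | Paired t, n=18 |
|---|---|---|---|---|---|---|---|
| SEE | 7 / 9 | 3.111 | 86% | 82.8% | 3.2 | 87.5% | 87.5% |
| BMI Z | 0.3 / 0.4 | 3.000 | 85% | 80.1% | 4.9 | 85.1% | 85.0% |
| Elastase | 120 / 150 | 3.200 | 88% | 84.8% | 3.2 | 89.3% | 89.2% |
| Calprotectin | 30 / 40 | 3.000 | 85% | 80.1% | 4.9 | 85.1% | 85.0% |
| Fatty acids (SD assumed mmol/L) | 2.0 / 2.8 | 2.857 | 80% | 76.1% | 3.9 | 81.5% | 81.5% |

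BMI Z and calprotectin fit the normal approximation at 16, or the t-test with all 18 evaluable. The other three match no column exactly.

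**Could rounded SDs explain it?** Solving the paired t-test at n=16 for the SD that returns each stated power gives 8.60 (SEE), 0.374 (BMI Z), 143 (elastase), 37.4 (calprotectin) and 2.67 (fatty acids). The first two would print as 9 and 0.4. Calprotectin would print as 40 only if rounded to the nearest ten. Elastase would print as 143 or 140, not 150, and fatty acids as 2.7, not 2.8. Rounding of the SDs can account for some of the figures but not all five.

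**Sensitivity of SEE to the effect (n=16, SD 9).**

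- 5.5 percentage points: λ = 5.5/9 × 4 = 2.444; paired t 62.8%, normal 68.6%. With all 18 evaluable the paired t gives 68.6%.
- 5.5% relative to a baseline of 115 (assumption): 0.055 × 115 = 6.325 points; λ = 2.811; paired t 74.8%, normal 80.3%.

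**Sensitivity to the SD (n=16, paired t).** Section 6.2 adds that "our recent experience with SEE measures in 1 year old healthy children showed a standard deviation of 8% in SEE percent predicted values", without saying that this is an SD of change. At SD 8 the power is 90.5% for 7 points and 72.9% for 5.5 points. At SD 10 (assumption) it is 74.5% and 53.9%.

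**Fatty acids at the reported change.** 10.2 − 8.5 = 1.7; λ = 1.7/2.8 × 4 = 2.429; paired t 62.2%, on the same unit assumption.

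**The case against.** **On the power figures.** For SEE, 86% lies between the two methods, and an unrounded SD near 8.6 would give it by the paired t-test. Both primary outcomes stay above 80% on the recomputed figures, so 16 evaluable children remain adequate for the planned effects. All of this stands, and it limits the weight of the point. It does not remove it, because SD rounding cannot explain all five figures and the largest gaps include BMI Z, a primary outcome.

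**On enrolling 18.** Section 6.2 says the extra two children cover attrition and also greater variability. If the planned 12% is lost, 18 × 0.88 = 15.84 remain, so the figure to quote is the one at 16.

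**On the SEE effect.** A reader might infer that SEE is really powered at 62.8%, or that Section 6.2 contradicts Section 1.1. The documents do not support either reading:

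- The 5.5% is an REE result at ages 5 to 61 years. The endpoint is SEE at 6 months to 2 years, where Section 1.1 says the effect is unexplored. It is a benchmark, not a forecast.
- Whether 5.5% means percentage points or a relative change is not stated. The planned fall is itself 7/115 = 6.1% in relative terms, so if 5.5% is relative, calling the two similar is fair.
- The 24 subjects (references 7 and 9) and the 23 (references 7 to 9) may or may not be one dataset.
- A planning effect need not equal an earlier observed mean.

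**Conclusion.** The point holds for the stated powers. On the printed inputs, the two-sided paired t-test at n=16 gives less than Section 6.2 states for SEE, BMI Z, elastase and calprotectin. It does so for fatty acids as well if the SD is 2.8 mmol/L for the change. The shortfall is 3.2 to 4.9 points. No primary outcome drops below 80%; fatty acids, a secondary outcome, do on that assumption. How the stated figures were obtained cannot be established from the document.

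The effect-size matter is secondary. Seven points is an assumption for this age group, neither supported by a printed figure nor disproved. The 62.8% and 74.8% figures are sensitivity values that depend on how 5.5% is read and on the SD of change staying at 9.

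All these figures concern the initial paired t-test at 12 weeks. Section 6.2 states no power for the signed-rank alternative or for the later mixed models.

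**What to change.** In Section 6.2 only:

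1. Restate all five powers by the two-sided paired t-test at n=16: SEE 82.8%, BMI Z 80.1%, elastase 84.8%, calprotectin 80.1%, and fatty acids 76.1% if the SD is confirmed as 2.8 mmol/L for the change. Alternatively, give the unrounded inputs and the method that produce the stated figures.
2. Correct the unit of the fatty acid SD and say whether it is an SD of the change.
3. Beside the 7-point SEE fall, print the prior REE result (5.5% of predicted, ages 5 to 61 years), say whether it is in percentage points, and label 7 points an assumption at 6 months to 2 years. Add the matching sensitivity power: 62.8% if percentage points, or 74.8% if relative to 115.
4. Print the reported fatty acid change of +1.7 mmol/L beside the planned +2.0.
5. Reconcile the 24 subjects with the 23 in the synopsis and Section 1.1, or say that they are different datasets.

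The cost is a few lines of text and less favourable stated power. Enrolment, endpoints and tests do not change.
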